14.4 Appendix D: Rai Staging System^a

Stage	Area of involvement	Risk Status
0	Lymphocytosis, lymphocytes in blood $>15 \times 10^9/\text{L}$ and $>40\%$ lymphocytes in bone marrow	Low
I	Stage 0 with enlarged node(s)	Intermediate
II	Stage 0-1 with splenomegaly, hepatomegaly, or both	Intermediate
III ^b	Stage 0-II with hemoglobin $< 11.0 \text{ g/dL}$ or hematocrit $<33\%$	High
IV ^b	Stage 0-III with platelets $<100 \times 10^9/\text{L}$	High

^a Research originally published in Blood. Rai KR et al. Clinical staging of chronic lymphocytic leukemia. Blood 1975;46(2):219-234. (c) The American Society of Hematology

^b Immune-mediated cytopenias are not the basis for these stage definitions.

14.5 Appendix E: Criteria for Response assessment in Acute Myeloid Leukemia (based on IWG and Cheson)

Disease assessments will be based on standardized response criteria as defined by the International Working Group (IWG) for AML (Cheson et al 2003).

Response classification in AML at a given evaluation time (Cheson 2003)	
Response category	Definition [#]
Complete remission (CR)	
Bone marrow $< 5\%$ blasts no blasts with Auer rods
 
Peripheral blood neutrophils $\geq 1.0 \times 10^9/\text{L}$ platelets $\geq 100 \times 10^9/\text{L}$ $\leq 1\%$ blasts No evidence of extramedullary disease (such as CNS or soft tissue involvement). Transfusion independent (see Section 7.2.1.4.5).
 
In case all criteria for CR apply and the patient receives platelet and/or neutrophil transfusions, the patient will be assessed as CRi.

Response classification in AML at a given evaluation time (Cheson 2003)	
Response category	Definition [#]
Complete remission with incomplete blood count recovery (CRI)	
Bone marrow < 5% blasts no blasts with Auer rods
 
Peripheral blood neutrophils < $1.0 \times 10^9/L$ and/or platelets < $100 \times 10^9/L$ ≤ 1% blasts No evidence of extramedullary disease (such as CNS or soft tissue involvement). Transfusion-independent (see Section 7.2.1.4.5). Exception: Platelet and neutrophil transfusions are allowed.

Partial Remission (PR)	
Bone marrow 50% or greater decrease (absolute range 5-25% blasts) < 5% of blasts contain Auer rods
 
Peripheral blood neutrophils < $1.0 \times 10^9/L$ and/or platelets < $100 \times 10^9/L$ No evidence of extramedullary disease (such as CNS or soft tissue involvement).

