Treatment failure	Treatment failure includes those patients for whom treatment has failed to achieve PR, CRI or CR throughout the treatment.
Relapse from CR or CRI*	Only in patients with a CR or CRI: Reappearance of blasts in peripheral blood (> 1%) OR ≥ 5% blasts in bone marrow OR (Re-)appearance of extramedullary disease
No response	In case a patient does not achieve CR, CRI, PR or relapse for an individual response assessment.
Unknown	In case the response assessment was not done, the baseline assessment was not done, the assessment was incomplete or was not done within the respective time frame.

[#] If not defined otherwise, all of the criteria apply.
 * Cheson et al (2003) does not specify relapse after PR but this may be considered in Phase I or II protocols.

Table 14-12 Exploratory AML response categories according to IWG

Response category	Definition
Cytogenetic complete remission (CRc)	All criteria for CR plus no cytogenetic abnormalities
Molecular complete remission (CRm)	All criteria for CRc plus no leukemic cells by RQ-PCR assay

14.6 Appendix F: Criteria for Response assessment in Acute Lymphoblastic Leukemia (based on NCCN Guidelines Version 1.2013)

Response classification in ALL for Blood and Bone Marrow at a given evaluation time	
Response category	Definition [#]
Complete remission (CR)	No circulating blasts or extramedullary disease (such as lymphadenopathy, splenomegaly, skin/gum infiltration, testicular mass, CNS or soft tissue involvement) Trilineage hematopoiesis (TLH) and < 5% blasts neutrophils $\geq 1.0 \times 10^9/L$ platelets $\geq 100 \times 10^9/L$ No recurrence for 4 weeks

Response classification in ALL for Blood and Bone Marrow at a given evaluation time	
Response category	Definition[#]
Complete remission with incomplete blood count recovery (CRi)	Peripheral blood Recovery of platelets but $< 100 \times 10^9/L$ or neutrophils is $< 1.0 \times 10^9/L$.
Progressive Disease (PD)	Increase of at least 25% in the absolute number of circulating or bone marrow blasts or development of extramedullary disease.
Treatment failure	Treatment failure includes those patients for whom treatment has failed to achieve a CR at the end of treatment
Relapse from CR or CRi*	Only in patients with a CR or CRi: Reappearance of blasts in peripheral blood ($> 1\%$) OR $\geq 5\%$ blasts in bone marrow OR (Re-)appearance of extramedullary disease

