14.12 Appendix L: Criteria for Response assessment in Myelodysplasia (based on modified IWG guidelines)¹

Category	Response Criteria
Complete remission	Bone marrow: $\leq 5\%$ myeloblasts with normal maturation of all cell lines* Persistent dysplasia will be noted* Peripheral blood 
 • Hgb ≥ 11 g/dL • Platelets $\geq 100 \times 10^9/L$ • Neutrophils $\geq 1.0 \times 10^9/L$ • Blasts 0%
Partial remission	All CR criteria if abnormal before treatment except: Bone marrow blasts decreased by $\geq 50\%$ over pretreatment but still $> 5\%$ Cellularity and morphology not relevant
Marrow CR	Bone marrow: $\leq 5\%$ myeloblasts and decrease by $\geq 50\%$ over pretreatment Peripheral blood: if HI responses, they will be noted in addition to marrow CR
Stable disease	Failure to achieve at least PR, but no evidence of progression for > 8 wks
Failure	Death during treatment or disease progression characterized by worsening of cytopenias, increase in percentage of bone marrow blasts, or progression to a more advanced MDS FAB subtype than pretreatment
Relapse after CR or PR	At least 1 of the following: 
 • Return to pretreatment bone marrow blast percentage • Decrement of $\geq 50\%$ from maximum remission/response levels in granulocytes or platelets • Reduction in Hgb concentration by ≥ 1.5 g/dL or transfusion dependence
Cytogenetic response	Complete - Disappearance of the chromosomal abnormality without appearance of new ones Partial - At least 50% reduction of the chromosomal abnormality
Disease progression	For patients with: 
 • Less than 5% blasts: $\geq 50\%$ increase in blasts to $> 5\%$ blasts • 5%-10% blasts: $\geq 50\%$ increase to $> 10\%$ blasts • 10%-20% blasts: $\geq 50\%$ increase to $> 20\%$ blasts • 20%-30% blasts: $\geq 50\%$ increase to $> 30\%$ blasts Any of the following: 
 • At least 50% decrement from maximum remission/response in granulocytes or platelets • Reduction in Hgb by > 2 g/dL • Transfusion dependence
*Dysplastic changes should consider the normal range of dysplastic changes (modification).	
¹ Cheson, et al. Clinical application and proposal for modification of the International Working Group (IWG) response criteria in myelodysplasia. blood-2005-10-4149.	

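### The AML partial-remission row in Appendix E requires a low neutrophil or platelet count, so a patient with a qualifying blast response and both counts recovered is scored No response

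*Protocol*

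**What the plan says.** Relapsed or refractory AML is eligible (protocol Section 5.2, criterion 8d), and Section 7.2.1.4 refers its response assessment to Appendix E. Counts below are in 10^9/L. The Appendix E table sets these categories:

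- **CR and CRi.** Both need marrow blasts below 5% and no Auer rods. CR needs neutrophils of at least 1.0 and platelets of at least 100. CRi applies when one or both are below those limits.
- **PR.** Marrow blasts: "50% or greater decrease (absolute range 5-25% blasts". Auer rods: "< 5% of blasts contain Auer rods". Peripheral blood: neutrophils below 1.0 and/or platelets below 100. No extramedullary disease.
- **Relapse.** "Only in patients with a CR or CRI".
- **No response.** The default for a patient who does not reach CR, CRi, "PR or relapse for an individual response assessment".
- **Treatment failure.** For a patient who never reaches PR, CRi or CR.

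A footnote to the definitions reads: "If not defined otherwise, all of the criteria apply". The table has no stable-disease row.

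The key secondary endpoint counts PR or better (protocol Table 3-1 and Section 10.5.1). SAP Section 6.1 defines clinical benefit for all tumours as CR, PR, or stable disease of at least 16 weeks.

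**The concern.** In the CRi row the low-count condition has a clear job: it separates CRi from CR when the marrow has cleared. In the PR row it has no counterpart. No other category takes a patient whose blasts have halved into the 5-25% range and whose blood counts are good, so cytopenia becomes a condition for being called a partial responder.

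Between two patients with the same marrow result, the one with better blood counts gets the worse category. Leukemia patients are exempt from the entry minimums for neutrophils and platelets (Section 5.2, criterion 11), but no upper limit applies. A patient who enters with both counts above the thresholds and keeps them can never be PR. A fall in either count on treatment could turn No response into PR.

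At stake are ORR, probably clinical benefit, and duration of response, which Section 10.5.2 limits to patients whose best response is PR or CR.

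**Working it through.** The plan gives no figure to reproduce; this is a check of a classification rule. The Appendix E rows were applied literally, with all criteria joined as the footnote requires.

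**Illustrative patient (assumed values).** Marrow blasts fall from 60% to 15%, with no Auer rods, no extramedullary disease and no prior CR or CRi. The blast criterion is met, since 15/60 = 25% of baseline is a 75% decrease and 15% lies within 5-25%. Only the counts are varied.

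| Neutrophils (rows), platelets (columns) | 40 | 99 | 100 | 160 |
|---|---|---|---|---|
| 0.5 | PR | PR | PR | PR |
| 0.99 | PR | PR | PR | PR |
| 1.0 | PR | PR | No response | No response |
| 1.8 | PR | PR | No response | No response |

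**Why the four cells fail.** With neutrophils 1.8 and platelets 160:

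1. Not CR or CRi, because 15% blasts is not below 5%.
2. Not PR, because neither count is low.
3. Not relapse, because there was no prior CR or CRi.
4. Hence No response. If the pattern persists, Treatment failure also applies.

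Of 16 combinations, 12 are PR and 4 are No response. The four are exactly those with neutrophils of at least 1.0 and platelets of at least 100. Recovery of one count alone leaves the patient PR, because the condition is and/or.

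**Alternative rules on the same grid.** With no count condition, 16 of 16 are PR. With CR-level counts required for PR, 4 of 16 are PR: the four now excluded qualify, and the twelve now PR do not.

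**Prior CR or CRi.** All 16 combinations are then relapse, because marrow blasts are at least 5%. The gap does not arise.

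**Size for ORR.** Protocol Section 5.1 plans 70-90 patients. One reclassified patient moves whole-cohort ORR by 1/90 = 1.1 to 1/70 = 1.4 percentage points.

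**The case against.** Several objections have weight.

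**The source criteria are not to hand.** Appendix E is based on published working-group criteria that cannot be consulted here. The protocol text alone shows a category boundary that runs the wrong way; it does not show what the source says. That stands, and it is why the row should be checked against the source. A reader might infer that the count line was copied from the CRi row. The two lines read alike, but the documents do not say how the text arose. A symbol lost in reading the PDF cannot be fully excluded either, although the CR row shows its at-least signs correctly and the and/or wording suits a low-count condition.

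**The MDS comparison is limited.** Appendix L starts its PR definition from "All CR criteria if abnormal before treatment except" and then relaxes the marrow blasts, the opposite direction to the AML row. MDS is a different disease with its own criteria, so this is a contrast within the protocol and not proof.

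**The effect could be overstated.** A reader might take the simulated accruals of 5 and 10 per cohort and infer a shift of 1/10 to 1/5, or 10-20 points, in a cohort's CBR and ORR. The documents do not support this. AML is not among the eight example cohorts of Appendix Q or the six named groups of SAP Section 10. In the SAP simulation it could enter only through Other, with an expected accrual of 2. Without the minimum enrolment and a control rate, it is left out of the Bayesian CBR analysis altogether. Likewise, not every partial responder is affected: both counts must have recovered, and there must be no prior CR or CRi.

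**Loss from clinical benefit is an inference.** The protocol never defines clinical benefit for AML explicitly. The loss follows from combining SAP Section 6.1 with the absence of a stable-disease row.

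**Investigators judge response.** SAP Sections 6.1 and 6.2 take the investigator's assessment and describe no programmed AML derivation. This does not remove the problem: a site that follows the table scores these patients as non-responders, and a site that overrides it does not.

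**Timing.** The SAP records early termination by the sponsor, with survival follow-up closed on August 4, 2016. The documents do not show whether any AML patient enrolled.

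**Conclusion.** The point holds as a defect in the response definition. For an AML patient without prior CR or CRi who meets the other PR criteria, the category turns from PR to No response exactly when neutrophils reach 1.0 and platelets reach 100. Such a patient is lost from ORR and, on the SAP's general definition, from clinical benefit.

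The size is modest and conditional on AML patients being enrolled. Whole-cohort ORR, the only ORR summary that protocol Section 10.5.1 foresees when groups have fewer than 10 patients, moves by about 1.1-1.4 points per patient at the planned 70-90. A larger shift is possible only in the descriptive row for each haematological tumour type under SAP Section 6.2, if AML has one with few patients. The primary Bayesian analysis is untouched unless AML meets the conditions for entering it.

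The conclusion rests on the Appendix E text as printed and on the footnote applying to the count line, which nothing in the PR row makes optional.

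**What to change.** Remove the low-count requirement from the PR row of Appendix E, so that patients with counts at or above the CR thresholds can qualify as PR. Check the row against the working-group criteria the appendix cites. State explicitly whether patients with low counts also remain PR: dropping the condition keeps them, whereas requiring CR-level counts would turn every patient now scored PR into No response, so the two repairs are not interchangeable.

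Apply the chosen rule wherever AML response is scored for ORR and CBR, and say in SAP Sections 6.1 and 6.2 how AML categories map to clinical benefit. Given the early termination, the report should state whether any AML patient was treated and, if so, whether any classification depends on this row.

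The cost is one table cell, a sentence or two in the SAP, and a check of any AML records. Marrow blasts and blood counts are already collected (protocol Sections 7.2.1.4.1 and 7.2.1.4.2).

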 - Patients with plasmacytoma must have a definite increase in the size; a definite increase is defined as a 50% (and at least 1 cm) increase as measured serially by the sum of the products of the cross-diameters of the measurable lesion
 - d. **Leukemia only:** Relapsed/refractory leukemia for which no standard therapy options are anticipated to result in a durable remission:

- Acute myelogenous leukemia (AML) by World Health Organization (WHO) classification or acute lymphoblastic leukemia (ALL) relapsed or refractory to standard chemotherapy; unsuitable for standard chemotherapy or unwilling to undergo standard chemotherapy. Philadelphia chromosome (Ph) positive ALL eligible if failed prior tyrosine-kinase inhibitor therapy.
 - Age > 60 years with AML not candidates for or have refused standard chemotherapy, excluding patients with acute promyelocytic leukemia (APL) or with favorable cytogenetic abnormalities [inv16, t(8;21)]
 - For patients with Chronic Myeloid Leukemia (CML) only accelerated and blast phase CML will be allowed
9. Patient has an Eastern Cooperative Oncology Group (ECOG) performance status ≤ 1 ([Appendix M](#))
 10. Patient has a life expectancy of at least 16 weeks
 11. Patients must have adequate bone marrow as described below:
 - a. Absolute Neutrophil Count (ANC) $\geq 1.5 \times 10^9/L$ (not applicable for leukemia patients)
 - b. Platelets (PLT) $\geq 75 \times 10^9/L$ (no platelet transfusion within past 14 days) (not applicable for leukemia patients)
 - c. Hemoglobin (Hgb) $\geq 8 \text{ g/dl}$ (not applicable for leukemia patients)
 12. Patient must meet the following laboratory values at the screening visit:
 - International Normalized Ratio (INR) ≤ 1.5
 - Serum amylase $\leq 2 \times \text{ULN}$
 - Serum lipase $\leq \text{ULN}$
 - Alkaline phosphatase (ALP) $\leq 5.0 \times \text{ULN}$
 - Fasting plasma glucose $\leq 175 \text{ mg/dL} (\leq 9.8 \text{ mmol/L})$
 13. All patients must have adequate organ function defined as described below:
 - a. Potassium, calcium (corrected for serum albumin), phosphorus and magnesium within normal limits (WNL). Supplementation is allowed to meet eligibility requirements
 - b. Serum creatinine $< 1.5 \text{ mg/dl}$ and/or calculated creatinine clearance (using Cockcroft-Gault formula) $\geq 30 \text{ mL/min}$

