No response	In case a patient does not achieve CR, CRi, PR or relapse for an individual response assessment.
Unknown	In case the response assessment was not done, the baseline assessment was not done, the assessment was incomplete or was not done within the respective time frame.

[#] If not defined otherwise, all of the criteria apply.

14.7 Appendix G: Criteria for Response assessment in Chronic Myelogenous Leukemia (based on NCCN Guidelines Version 4. 2013)

Response classification in CML for hematologic, cytogenetic, and molecular evaluation at a given evaluation time	
Response category	Definition[#]
Complete hematologic response (CR) ¹	Complete normalization of peripheral blood counts with leukocyte count $< 10 \times 10^9/L$ platelets $< 450 \times 10^9/L$ No immature cells such as myelocytes, promyelocytes, or blasts in peripheral blood No signs and symptoms of disease with disappearance of splenomegaly
Cytogenetic response ^{2,3}	Complete No Ph-positive metaphases Partial $1\% - 35\%$ Ph-positive metaphases Major $0\% - 35\%$ Ph-positive metaphases (complete + partial) Minor $> 35\%$ Ph-positive metaphases
Molecular response ^{4,5}	Complete No detectable BCR-ABL mRNA by QPCR using an assay with a sensitivity of at least 4.5 logs below standardized baseline. Major ≥ 3 log reduction in international scale of BCR-ABL mRNA
Treatment failure	Treatment failure includes those patients for whom treatment has failed to achieve a complete hematologic response (CR) throughout treatment.
No response	In case a patient does not achieve CR, PR or relapse for an individual response assessment.
Unknown	In case the response assessment was not done, the baseline assessment was not done, the assessment was incomplete or was not done within the respective time frame

Response classification in CML for hematologic, cytogenetic, and molecular evaluation at a given evaluation time	
Response category	Definition[#]

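### The ALL definition of CRi in Appendix F has no blast or extramedullary condition, so read literally a neutropenic patient with unchanged blasts is classified CRi instead of No response

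*Protocol*

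**What the plan says.** The CRi row of Appendix F (Protocol 14.6) sits under a peripheral-blood label. It consists of "Recovery of platelets but $< 100 \times 10^9/L$ or neutrophils is" below 1.0 × 10^9/L, and nothing more. The CR row directly above asks for much more: no circulating blasts, no extramedullary disease, "Trilineage hematopoiesis (TLH) and < 5% blasts", recovered neutrophils and platelets, and no recurrence for 4 weeks. A footnote to the table reads "If not defined otherwise, all of the criteria apply".

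The other rows of Appendix F that bear on the point are these:
- Progressive disease needs a rise of at least 25% in circulating or marrow blasts, or new extramedullary disease.
- No response is the residual category for patients who do not reach CR, CRi, PR or relapse.
- Treatment failure is judged on CR alone.
- There is no PR row and no SD row.
- The relapse row, which Appendices E and F share, opens "Only in patients with a CR or CRI: Reappearance of blasts in peripheral blood". Its thresholds are more than 1% blasts in blood or at least 5% in marrow.

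In Protocol 5.2 item 11, the neutrophil, platelet and hemoglobin limits are each marked "not applicable for leukemia patients". Item 14 allows peripheral blasts up to 50,000/mm³.

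Relapse is a PFS event in Protocol 10.5.2 and SAP 6.3. ORR is PR or greater in Protocol Table 3-1 but PR plus CR in Protocol 10.5.1. DOR applies to a best response of PR or CR (Protocol 10.5.2). Clinical benefit is CR, PR or SD of at least 16 weeks (SAP 6.1). None of these definitions mentions CRi.

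**The concern.** A response category should describe a state that the disease does not already satisfy at entry. The ALL CRi row describes low counts, which active leukemia can itself produce, and the waived entry limits admit patients with such counts. Applied as printed, the rule can label untreated-looking disease as a form of complete remission.

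Two things are at stake. First, a patient who should be No response leaves that category. Second, once labeled CRi, the patient falls under the relapse row, whose blast thresholds are already met. Relapse counts for PFS, so stable disease could be recorded as an event that the progression criterion would not have produced. A neutropenic patient whose blasts are rising could also meet CRi and progressive disease at one visit, and the appendix gives no order of precedence.

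**Working it through.** No sample size, power or error rate depends on this row, and the plan states no figure to reproduce. The check sets the definitions side by side and applies them to one record.

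**1. Disease-burden conditions by category**

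| Category | Marrow | Blood blasts | Extramedullary or tumor burden | Persistence |
|---|---|---|---|---|
| ALL CR (App. F) | <5% blasts | none | no extramedullary disease | 4 weeks |
| ALL CRi (App. F) | not stated | not stated | not stated | not stated |
| AML CRi (App. E) | <5% blasts, no Auer rods | ≤1% | no extramedullary disease | not stated |
| CLL CRi (App. H) | hypocellular | not stated | Group A: no node >1.5 cm, no organomegaly | not stated |

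Only the ALL row has no disease-burden entry. The footnote does not import the missing conditions. It says that listed criteria apply jointly, not that one row inherits from another. The AML table carries the same footnote and still repeats "Bone marrow $< 5\%$ blasts no blasts with Auer rods" within its own CRi row.

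**2. Literal application.** Hypothetical ALL patient, allowed by Protocol 5.2: neutrophils 0.8 × 10^9/L and marrow blasts 40%, both unchanged from entry.
- CR: no, since 40% exceeds 5%.
- CRi: yes, through the neutrophil clause after the word or, since 0.8 < 1.0.
- Progressive disease: no, since the blast rise is 0% against the required 25%.
- No response: unavailable, because CRi is met.
- Relapse thresholds: already met, since 40% ≥ 5%.

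**3. Same patient with the CR row's clearance conditions added to CRi.** CR no, CRi no, progressive disease no, so No response. The relapse row no longer applies. The classification turns entirely on the missing conditions.

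**4. Sensitivity to the wording.** If the word recovery is taken to govern both clauses, the unchanged patient above no longer qualifies. A patient whose platelets rise to 60 × 10^9/L from a lower entry value, with marrow blasts still at 40%, would qualify. That reading narrows the gap but supplies no blast criterion.

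**5. Size, if CRi were counted as response.** One misclassified patient moves a rate by 1/n. For an assumed 1 to 3 ALL patients, the ALL rate moves by 1/1 = 100 points to 1/3 = 33 points. Across the planned 70 to 90 patients, it moves by 1/70 = 1.4 to 1/90 = 1.1 points.

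**The case against.** The case for leaving the row alone has real substance.

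- **Intent is visible.** The category is named as a complete remission, and relapse from it is described as blasts reappearing, which presupposes that they had cleared. An investigator holding a marrow report of 40% blasts is unlikely to record CRi. This stands, and it is the main reason the practical effect is probably small. It does not make the printed rule correct.
- **Marrow is part of assessment.** Protocol 7.2.1.4 bases ALL response on blood and marrow together and treats response as not assessable when the two are more than 5 days apart. That limits assignment from blood alone. It does not repair the row, because the CRi definition gives the marrow result no role. Protocol 7.2.1.4.2 names CR, not CRi, as the response that marrow confirms.
- **Layout.** The row follows a repeated table header and has a blood label with no marrow counterpart, so a line lost in PDF conversion cannot be excluded. Nothing shows that one was, but the source layout should be checked.
- **Endpoint harm.** A reader might infer that CRi is scored as a response and so inflates ORR, DOR or the primary CBR. The documents do not support that. No section maps CRi to any of them, ORR is worded in two ways, and the ALL treatment-failure row credits only CR. A reader might also infer a study-level rate of false remission equal to the share of neutropenic ALL patients. The documents give no such share, so no rate can be stated.

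**Conclusion.** The point holds as a defect in a stated rule: the ALL CRi row omits the disease-clearance conditions that its own CR row and the parallel AML definition contain. On the literal reading it moves a patient from No response to CRi and exposes that patient to a false PFS event. A false response follows only if CRi is treated as PR or greater, which is undefined.

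The effect is per patient and probably small. ALL is not among the expected tumor types in Protocol 5.1 or the groups in SAP 10.1. An unlisted group needs at least 3 or 4 patients (the documents vary) and a usable control rate before it enters the Bayesian analysis. If no ALL patient was enrolled, the point has no effect on the results. The conclusion assumes that the row is printed in full. The worked example also assumes that the neutrophil clause stands apart from the word recovery.

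**What to change.** Redefine ALL CRi as meeting the ALL CR row's conditions (no circulating blasts, no extramedullary disease, marrow blasts below 5%, no recurrence for 4 weeks), except that platelets are below 100 × 10^9/L and/or neutrophils are below 1.0 × 10^9/L. The 4-week condition comes from the ALL CR row; Appendix E has no such condition for AML CRi, and it also tolerates up to 1% blood blasts.

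Two companion changes are needed. Make the marrow-confirmation wording in Protocol 7.2.1.4.2, and any matching entry in Table 7-1, consistent with a marrow criterion for CRi. State in Protocol 10.4 and 10.5 and SAP 6.1 and 6.2 whether CRi counts toward CBR, ORR and DOR.

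The cost is one table cell, one sentence on marrow confirmation and one sentence on mapping, plus a marrow result where CRi is to be claimed. CRi becomes harder to assign. Because the SAP records that the study ended early, the same rule could be set out in the SAP's response derivation and applied to any ALL patient before analysis.
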